Screening questions that warrant follow up if the participant answers "yes":

- Have you been diagnosed with a methamphetamine use disorder? (follow up- providers to determine if participant should have a methamphetamine use diagnosis, if not currently diagnosed)
- Are you claustrophobic or afraid of small, closed-in spaces? (follow-up- participant needs to confirm that they can handle being in an MRI machine through additional questions)
- Do you have a problem with loud noises? (follow-up- participant needs to confirm that the noises from the MRI are not too loud through additional questions)
- Have you ever had a neurosurgical procedure? (follow up- type of procedure matters)
- Have you been diagnosed with another neurological disorder? (follow-up- type of disorder matters)
- Are you able to make it to all visits for this study without assistance?
Additional information: This involves a baseline visit, then visits five days a week for two weeks and three days a week for two more weeks. The visits need to take place Monday through Friday, but we can start most any day depending on what's convenient for you. There will also be follow-up visits that can be completed by phone or in person one month and two months after the other visits are completed.
 - If not, Please explain any additional services you may need to get to and from study appointments, (i.e. transportation)

Randomization

The randomization scheme was block randomization stratified by study site, with block sizes of 4 and a 1:1 ratio, designed to ensure approximate balance in the number of subjects. Subjects are randomized to receive stimulation at the DLPFC or MPFC first, although both groups receive stimulation at both sites at each visit. The subject is assigned to a group at the first TMS treatment visit.

Intervention

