TMS treatment using theta burst stimulation will be provided 5 days in the first week, five days in the second week, and three times per week in weeks 3 and 4. The start day will be somewhat flexible. Subjects will participate in 5 treatment sessions in each of the first two 7-day periods, and three treatment sessions in each of the third and fourth 7-day periods (treatment weeks). Theta burst stimulation can be completed in as little as 3 minutes per treatment (two sites), so these visits should take roughly 15-20 minutes total when once-weekly additional assessments are not being completed. We will measure blood pressure and pulse prior to each treatment. If systolic blood pressure exceeds 160 mmHg, diastolic blood pressure exceeds 100 mmHg, or pulse exceeds 110 beats per minute, then we will confirm this with a second measurement. If it is confirmed by a second measurement, then the treatment will be withheld, and a clinician contacted to assess the patient. Before each treatment, we will also ask the subject when they last used methamphetamine. Treatment may be withheld if it is too recent to minimize risk of adverse effects, particularly seizure. Participants will be asked to report craving using a single question before and after each treatment. Participants will only be asked to report any adverse event experiences at these visits.

On the last day of TMS in each treatment week when TMS is administered, the subject will be asked to complete additional assessments. At 1 week, 2 weeks, and 3 weeks, these will involve completion of surveys. At weeks 1 and 3 only the Brief Substance Craving Scale will be administered, while additional survey instruments will be administered after week 2. These visits will also involve reporting of the number of days in the last week in which they used methamphetamine as well as whether they remain engaged in a psychosocial treatment and what treatments (partial hospitalization, intensive outpatient, outpatient medical, outpatient psychotherapy, group therapy, other, none). If they were engaged in partial hospitalization or intensive outpatient treatment, we will ask whether they completed the planned course of treatment or stopped early.

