After the last treatment in week 4, the subject will be asked to again complete all assessment instruments, provide information on substance use in the last week, complete the psychological tests, submit a urine drug screen (if there is not a recent result on file in their EHR), and complete fMRI imaging. If the subject elects

to participate in the optional EEG and timing task, this will add about an hour to this visit. If they elect to participate in this optional EEG and task, we will be adhering electroencephalogram (EEG) leads to their scalp and then have them perform 2 blocks of the interval timing task where they estimate the passage of a specified (3 or 12 second) passage of time (~22min - 11 min blocks). The beginning of the trial is indicated by the presentation of either a 3 or a 12 on the computer screen which also indicates the duration of time the subject should estimate. During performance, we will collect electroencephalographic data from patients which will be analyzed offline.

TMS treatment will end at this time. We will then plan follow-up visits at 8 weeks and 12 weeks after the start of treatment, which can be completed by phone/online or in person base on the subject's preference. At these visits subjects will complete the survey-based assessments. They will also be asked about the number of days of methamphetamine use in the last week and their current psychosocial treatment modality.

An example study schedule and full list of assessments I provided below.

Figure 1: Example Study Schedule

Study Week	Monday	Tuesday	Wednesday	Thursday	Friday
1	First visit: determine eligibility to continue, questionnaires, psychological testing, urine drug screen if needed, MRI, optional EEG (3-5 hours)				
1	TMS	TMS	TMS	TMS	TMS, questionnaires, urine sample if needed (about 30 minutes)
2	TMS	TMS	TMS	TMS	TMS, questionnaires, urine sample if needed (45-60 minutes)
3	TMS		TMS		TMS, questionnaires, urine sample if needed (about 30 minutes)
4	TMS		TMS		TMS, questionnaires psychological testing, urine sample if needed, MRI, optional EEG (3-5 hours)
8	One follow-up visit or phone call to complete questionnaires (45-60 minutes)				
12	One follow-up visit or phone call to complete questionnaires (45-60 minutes)				

Figure 2: Schedule of study assessments by visit

Measure	Time to complete (minutes)	First Visit	Last TMS day week 1	Last TMS day week 2	Last TMS day week 3	Last TMS day week 4	Week 8	Week 12

Interview Questions								

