Personal information, medical history, substance use history	20	x						
Report substance use and current treatment	2	x	x	x	x	x	x	x
Urine drug screen (if needed)	10	x	x	x	x	x		
Mini International Neuropsychiatric Interview	20	x						
Written Questionnaires								
Brief Substance Craving Scale	5	x	x	x	x	x	x	x
Assessment of Recovery Capital	5-10	x				x	x	x
Brief Addiction Monitor	10	x				x	x	x
Quality of Life Enjoyment and Satisfaction Questionnaire—Short Form	5	x		x		x	x	x
Patient Health Questionnaire	3	x		x		x	x	x
Generalized Anxiety Disorder 7-item scale	2	x		x		x	x	x
Positive and Negative Affect Scale	5-10	x		x		x	x	x
Pittsburgh Sleep Quality Index	5-10	x		x		x	x	x
Big Five Inventory-2	5-15	x						
UPPS-P Impulsive Behavior Scale	15	x				x		
Difficulties in Emotion Regulation Scale-Short-Form	5	x				x		
Monetary Choice Questionnaire	5	x				x		
Psychological Testing								
Flanker Inhibitory Control and Attention	3-5	x				x		
Imaging								
MRI	60-90	x				x		
EEG and Timing Task (optional)	60	x				x		

Procedures for contacting subjects lost to follow-up

The subject will be called or texted (per their preference) up to 5 times after each loss to follow-up with two days between contacts and messages left to contact the research assistant if voice messaging is available. If the subject provided a secondary contact person that individual will be called up to three times with two days between calls and voice messages left if available, starting after the third failed attempt to contact the subject. We will inform that person that we are trying to reach the study subject about a research study and the subject said they might be able to help us find them, without disclosing the details of the study or the subject's health conditions. If the secondary contact is reached, they will be asked if they know the whereabouts of the person, if they could reach out to them, and for new contact information if that has changed. If the secondary contact provides information saying that the person cannot be reached for a particular reason, then this will be documented in the record. If the subject is said to be deceased, then the secondary contact will be asked if they know the circumstances of the death.

Expected Risks of Participation

TMS Risks

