This is a pilot study without an untreated control group so will not be able to establish that the treatment is causal in improving outcomes. The overarching goal is to evaluate the ability to recruit and retain subjects, establish safety of the intervention in this population, evaluate target engagement of TMS using fMRI, and to determine the extent to which patient symptoms and substance use appear to improve during participation in treatment. We anticipate approximately 20 subjects, which should be adequate to statistically detect clinically meaningful changes in symptoms and other outcome measures, depending on attrition. We will randomize order of treatments to gather preliminary data on any differences, but do not anticipate power to detect significant differences in effect by order of treatment with this sample size.

Outcomes

Primary outcomes:

1. Retention in the Study: Measured from Baseline to 12 weeks
2. Retention in Psychosocial Treatment: Measured from Baseline to 18 days (self-reported)

Secondary outcomes (used all available data points as specified in figure 2):

1. Functional Connectivity of the Dorsolateral Prefrontal Cortex and Anterior Insula—change from baseline to 4 weeks. Measured by correlation of region activity over MRI time series data, averaged for left and right hemisphere.
2. Functional Connectivity Dorsolateral Prefrontal Cortex and Anterior Cingulate Cortex—change from baseline to 4 weeks. Measured by correlation of region activity over MRI time series data, averaged for left and right hemisphere.
3. Functional Connectivity of the Medial Prefrontal Cortex and Ventral Striatum—change from baseline to 4 weeks. Measured by correlation of region activity over MRI time series data, averaged for left and right hemisphere.
4. Kirby Delay Discounting Questionnaire, 27 Item

5. Number of Days of Methamphetamine Use in the Past Week
6. Urine Drug Screen Positive for Stimulant
7. Brief Substance Craving Scale
8. Brief Addiction Monitor—Use Subscale
9. Brief Addiction Monitor—Risk Factors Subscale
10. Brief Addiction Monitor—Protective Factors Subscale
11. Brief Addiction Monitor—Satisfaction with Progress Toward Achieving Recovery Goals (question 17)
12. Quality of Life Enjoyment and Satisfaction Questionnaire—Short Form
13. Patient Health Questionnaire--8 Item Scale
14. Generalized Anxiety Disorder 7-item Scale
15. Assessment of Recovery Capital
16. Positive and Negative Affect Scale—Positive Affect Score

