17. Positive and Negative Affect Scale—Negative Affect Score
18. Pittsburgh Sleep Quality Index
19. Difficulties in Emotion Regulation Scale--Short Form
20. UPPS-P Impulsive Behavior Scale, 59-item Revised Version

Safety outcomes

Adverse events are reported at each TMS treatment visit, or if otherwise volunteered by subject.

Populations to be analyzed

Intention to treat: Subjects will be analyzed in the groups they were randomized to. However, only complete data will be used, and subjects were discontinued from the study if they missed more than 4 TMS treatments.

Analyses

Descriptive statistics will be examined for demographic and other variables, overall and by intervention group.

For other analyses, a fixed time will be assigned for each study visit, which approximates the time at which the visit would have occurred on a typical study schedule.

Primary outcomes

The primary analysis will compare intervention groups (DLPFC first or MPFC first) on time to discontinuation in the study and time to discontinuation of psychosocial treatment. The latter is defined as a participant indicating they are no longer in or seeking treatment. All subjects were in treatment or planning treatment at baseline, as an inclusion criterion. Time retained in the study or treatment will be described using Kaplan-Meier curves, and intervention groups will be compared using log-rank tests.

Secondary outcomes

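### The psychosocial-retention primary outcome is defined only to day 18, before TMS ends, while later status reports are scheduled and the analysis text sets no horizon

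*Combined protocol and SAP*

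**What the plan says.** The SAP lists two primary outcomes with different horizons: "Retention in the Study: Measured from Baseline to 12 weeks" and "Retention in Psychosocial Treatment: Measured from Baseline to 18 days (self-reported". Neither the list nor the rest of the document explains the shorter one.

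Under Analyses, both are time-to-event outcomes, described by Kaplan-Meier curves and compared between order groups by log-rank test. The psychosocial event occurs when a participant reports being neither in treatment nor looking for it. That paragraph names no end point. For timing, "a fixed time will be assigned for each study visit", but the times are not listed. The Missing data section uses all available data as far as feasible and does not impute.

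On the schedule, Study Procedures sets five sessions in each of the first two weeks and "three treatment sessions in each of the third and fourth 7-day periods (treatment weeks". The screening section adds: "The visits need to take place Monday through Friday". TMS starts on the day of the baseline visit or within a week after it.

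Treatment status is scheduled beyond day 18. In Figure 2 the row "Report substance use and current treatment" is marked at the first visit and at weeks 1, 2, 3, 4, 8 and 12. For the later contacts, Study Procedures says "We will then plan follow-up visits at 8 weeks and 12 weeks after the start of treatment", and there subjects are asked about "the number of days of methamphetamine use in the last week and their current psychosocial treatment modality".

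**The concern.** The trial is a feasibility pilot in people receiving psychosocial treatment, and staying in that treatment is one of its two primary outcomes. A reader will want to know how many were still in it when stimulation finished and during the months afterwards. An 18-day window stops short of both, although the other primary outcome runs to 12 weeks and the status item is scheduled to week 12. At stake is the usefulness of a primary descriptive estimate for planning a later trial.

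**Working it through.** **Inputs.** 16 sessions, as 5, 5, 3 and 3 in successive 7-day periods, on weekdays, with any starting weekday (Study Procedures, screening section, Figure 1). Baseline 0 to 7 days before first TMS (Study Procedures). Six post-baseline status reports, at weeks 1, 2, 3, 4, 8 and 12 (Figure 2). About 20 subjects (Sample Size Justification).

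**1. Where 18 days could come from.** On Figure 1, with baseline and first TMS both on day 0, sessions fall on days 0–4, 7–11, 14, 16, 18, 21, 23 and 25. The last TMS days of weeks 1 to 4 are days 4, 11, 18 and 25. Day 18 is then exactly the week-3 visit, with 5 + 5 + 3 = 13 of 16 sessions given (81%). This mapping is an inference, because the SAP does not list its fixed visit times.

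**2. What changes if baseline is earlier.** The same grid, counted from baseline:

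| Days from baseline to first TMS | Last TMS day of weeks 1–4 | Sessions by day 18 | Weekly reports by day 18 |
|---|---|---|---|
| 0 | 4, 11, 18, 25 | 13 | 3 |
| 1 | 5, 12, 19, 26 | 12 | 2 |
| 3 | 7, 14, 21, 28 | 11 | 2 |
| 7 | 11, 18, 25, 32 | 10 | 2 |

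Calling first TMS day 1 gives the second row. Every alternative puts the cut-off earlier in the course.

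**3. Whether TMS can end by day 18.** With first TMS as day 0, the fourth 7-day period covers days 21 to 27. By starting weekday, the last of its three sessions can fall on days 23–25 (Monday), 23–27 (Tuesday or Wednesday) or 25–27 (Thursday or Friday). The overall range is day 23 to 27. Counted from baseline it is the same or later, so day 18 precedes the planned end of TMS on every schedule.

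**4. How much lies outside the window.** Taking the nominal days as 4, 11, 18, 25, 56 and 84, three of the six reports come after day 18, as do 3 of 16 sessions. The window covers 18/84 = 21% of the 12-week horizon. One place in Study Procedures puts the last two contacts at study weeks 9 and 13 instead; they are outside the window either way.

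**5. Illustration of the horizon, under assumed rates.** The documents give no discontinuation rate. Suppose 20 subjects, a constant hazard, no loss, and a 12-week discontinuation probability D. Expected events by day 18 are 20 × [1 − (1 − D)^(18/84)]:
- D = 20%: 0.9 events by day 18, against 4 by day 84 (23%).
- D = 60%: 3.6 events by day 18, against 12 by day 84 (30%).

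**6. Illustration of censoring, a separate matter.** Because the event needs a report from the participant and nothing is imputed, those lost would be censored. Suppose 5% of those seen leave treatment at each visit and 10% are permanently lost. At three visits Kaplan-Meier gives 0.95^3 = 86%, while counting all lost as discontinued gives (0.95 × 0.90)^3 = 0.855^3 = 63%. At six visits the values are 0.95^6 = 74% and 0.855^6 = 39%. These figures explain why a sensitivity analysis is wanted. They rest on assumed rates and do not measure the 18-day problem.

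**The case against.** The strongest reply is that the trial is not confined to 18 days. The Kaplan-Meier paragraph has no horizon and the missing-data rule uses all available data, so the analysts could carry the curve to week 12. This stands against the stronger reading a reader might infer, that the plan makes later retention impossible to describe. It does not remove the point: the outcome definition and the analysis text then disagree about the window of a primary outcome.

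Second, the later data are thinner than Figure 2 suggests. The week-4 text in Study Procedures names substance use but not psychosocial treatment, so week 4 rests on the Figure 2 row and on a broad reading of the paragraph about weekly assessments. The engagement question there follows a list of weeks 1 to 3, which might even explain the 18-day limit, though no document says so. Weeks 8 and 12 record only the current modality, which does not show whether someone with none is still seeking treatment. This stands, and the extension needs a stated classification rule. It does not defeat the extension, because the weekly question as described does not mention seeking either.

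Third, no progression criterion depends on this outcome, and study retention is already followed to 12 weeks. That limits the consequence. One might also infer that the comparison of treatment order is compromised. The documents do not support that: the same rules apply to both groups, and Sample Size Justification already says power for order differences is not expected.

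**Conclusion.** The point holds as a mismatch in the plan and a shortfall in one descriptive primary estimate. The 18-day limit, the lack of a stated reason, and its falling before the planned end of TMS (day 23 to 27 after first TMS) are firm. The match to the week-3 visit and to 13 of 16 sessions depends on baseline and first TMS both being day 0; otherwise 10 to 12 sessions have been given and the week-3 report falls outside too. At least 3 of 6 scheduled post-baseline reports lie beyond the window.

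If the definition is followed as written, the outcome does not describe retention in psychosocial treatment to the end of TMS or during follow-up. The event wording is not itself an error: counting people who are still seeking treatment mirrors the inclusion criterion. This should be fixed, but it does not undermine the trial.

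**What to change.** - Keep the 18-day value and say why 18 days was chosen.
- Also report the Kaplan-Meier retention estimate through week 4 and through week 12, from the reports already scheduled.
- Reconcile the outcome list, the Analyses text, the week-4 and follow-up text in Study Procedures, and Figure 2, so that one horizon and one set of status visits is stated. List the fixed visit times and the day-0 convention.
- State how a report of no current treatment is classified. One way is to show results with it counted as discontinued and again as still seeking.
- Add one sensitivity analysis counting loss to follow-up as discontinuation. With about 20 subjects, each person lost before the cut-off moves that figure by 1/20 = 5 points.
- Label the additions post hoc if outcome data have been seen.

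Tables by modality, or separating program completers from early stoppers, are optional and would be sparse at this sample size.

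The cost is a few SAP sentences and table rows, with no new visits. The later retention figures will probably be lower than the 18-day figure, more subjects will be censored by week 12, and the log-rank comparison of order will still have little power.

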The study intervention is open-label dual-target theta burst stimulation delivered in sequential fashion to the DLPFC and the MPFC. The order of treatments is determined by the randomization scheme, but the treatments are otherwise identical. Treatment targeting will occur at the Beam F3 and FP1 scalp regions as defined by the 10-20 EEG system. A Magventure MagPro X100 figure-8 coil with theta burst capabilities will be used to deliver the stimulus, including intermittent theta burst stimulation to the DLPFC (2 seconds of 50-Hz triplets delivered at 5 Hz, 8 seconds intertrain interval, 600 total pulses) and continuous theta burst to the MPFC (continuous 50-Hz stimulation triplets, 600 pulses). Stimulation will be delivered at 110% of the resting motor threshold, as determined by the stimulation threshold at which single-pulse TMS stimulation over the motor cortex hand knob region can elicit visible finger movement on 3 of 5 trials, with stimulation dose adjustment for distance from target to coil as needed. Treatment sessions will consist of a single treatment protocol at each stimulation site. Sessions will occur 5 times per week for the first 2 weeks, followed by 3 sessions per week for an additional 2 weeks (16 treatment sessions total).

Study Procedures

This study lasts for a total of 12-13 weeks, and involves 19 visits. Although visits vary from 15 minutes to 5 hours, they average 45-50 minutes. The first week involves a baseline visit that will take 3-4 hours. If the subject elects to participate in the optional EEG and timing task, this will add about an hour to their first visit. Subjects will receive 4 weeks of TMS treatments, and each treatment should take about 15 minutes. The first two weeks of treatment involve 5 visits per week

where the subject receives TMS. The third and fourth weeks of treatment involve 3 visits per week where the subject receives TMS. Additional assessments are done on the last treatment day of each treatment week. These visits, including treatment time, will take about 30 minutes after the first and third weeks of treatment, 45-60 minutes after the second week of treatment, and 3-4 hours after the fourth week of treatment. If the subject elects to participate in the optional EEG and timing task, this will add about an hour to their visit after the fourth week of treatment. Follow-up phone calls lasting 45-60 minutes will take place 4 weeks and 8 weeks after the end of TMS treatment (week 9 and week 13 of the study).

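### Adverse events are solicited only at TMS visits, so all time after a participant's last attended session rests on volunteered reports

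*Combined protocol and SAP*

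**What the plan says.** The SAP, under Safety outcomes, gives one sentence: "Adverse events are reported at each TMS treatment visit, or if otherwise volunteered by subject". The protocol, under Study Procedures, describes the routine treatment visits and says: "Participants will only be asked to report any adverse event experiences at these visits".

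For the two contacts after treatment, the same section says: "At these visits subjects will complete the survey-based assessments". It adds questions on recent days of methamphetamine use and current psychosocial treatment, and nothing on adverse events. The procedure for subjects lost to follow-up sets out repeated calls or texts. The only health event it asks about is a death, whose circumstances are sought from a secondary contact who reports one.

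The SAP, under Sample Size Justification, includes in the overarching goal to "establish safety of the intervention in this population". Under Populations to be analyzed, participants who miss more than 4 treatments leave the study. Under Missing data, the plan expects dropout.

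**The concern.** The plan follows people for 12 weeks but asks about harm for roughly the first 4. It also ties the question to attendance. If an adverse event is what keeps someone away, it may occur or worsen after the last attended session, which is when active questioning ends. Volunteered reporting generally finds fewer events than asking does, so the likely error is a safety summary that looks cleaner than it should. With no question at weeks 8 and 12, an absence of late events cannot be told apart from an absence of asking. The results are meant to help justify a controlled trial, so that distinction matters to whoever designs it.

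**Working it through.** **Inputs.** Treatment sessions per week are 5, 5, 3 and 3 (protocol, Intervention). On the calendar, the protocol says "This study lasts for a total of 12-13 weeks, and involves 19 visits" and "We will then plan follow-up visits at 8 weeks and 12 weeks after the start of treatment". The window for study retention is given in the SAP as "Retention in the Study: Measured from Baseline to 12 weeks". Planned size is about 20 (SAP, Sample Size Justification).

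**The plan's own counts.**
- Sessions: 5 + 5 + 3 + 3 = 16, as stated.
- Visits: 1 baseline + 16 treatment + 2 follow-up = 19, as stated.

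**Share of calendar time without solicited reports, for a completer.**
- Main figure: (12 − 4)/12 = 8/12 = 66.7%.
- Over 13 weeks: 8/13 = 61.5%, or 9/13 = 69.2% if the baseline week is also counted as unsolicited.
- By days on the Monday-to-Friday example, the last session falls 25 days after the first: (84 − 25)/84 = 59/84 = 70.2%.

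The range is 62% to 70%, so about two thirds is fair for calendar time.

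**Share of visits.** From first treatment onward there are 16 + 2 = 18 visits. The question is asked at 16 and not at 2: 2/18 = 11%.

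**Person-weeks at 20 completers.** Solicited: 20 × 4 = 80 of 20 × 12 = 240 (33.3%). Volunteered only: 160.

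**Effect of dropout.** The documents give no dropout rate, so this part is an assumption. If a fraction d stops at week w, solicited person-weeks are 20(1 − d) × 4 + 20 × d × w.
- d = 0.2, w = 3: 64 + 12 = 76, or 31.7% of 240.
- d = 0.5, w = 1: 40 + 10 = 50, or 20.8% of 240.

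**What a discontinuer has.** Group assignment takes place at the first treatment visit (protocol, Randomization), and adverse events are asked about at each such visit. A treated participant therefore has one solicited report per session attended. Someone removed for missing more than 4 of 16 has missed at least 5, so has attended at most 16 − 5 = 11. Solicited reports then number from 1 to 11, with none after stopping.

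**A point the text leaves open.** It does not say whether the question comes before or after stimulation. If before, a person who leaves after one session has no solicited report following exposure, and no completer has one following session 16.

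**The case against.** The best case for the plan has five parts.

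- *Exposure is covered.* All stimulation falls inside the solicited window, and the protocol's TMS Risks section places the common effects during stimulation. This stands, and it is why 67% of calendar time must not be read as 67% of safety information.
- *Weeks 8 and 12 are not blind.* The Patient Health Questionnaire, GAD-7, sleep index, affect scale and Brief Addiction Monitor are all given then (Figure 2). This stands in part. They follow some symptoms, but the plan does not designate them as adverse-event collection, and they do not take the place of an event record with date and seriousness.
- *The text is less clear than it looks.* The word "only" in the Study Procedures sentence may limit what is asked at routine visits and not where events are asked about. Figure 2 has no adverse-event row, but it has none for the treatment days either, where the question is certainly asked, so its silence proves little. Both remarks are right. The point rests instead on the SAP sentence, which separates reporting at treatment visits from volunteered reporting, and on the described content of the follow-up contacts.
- *Safety is not a listed objective or primary outcome*, and the protocol leaves evaluation of efficacy and safety to a later trial. True, but the SAP names establishing safety in its overarching goal.
- *Discontinuers may not be reachable*, so items at weeks 8 and 12 may miss them. True, so the remedy must also use contacts made after a participant stops attending.

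A reader might infer that early discontinuers have no solicited reports at all. The documents do not support that: every treated participant is asked at each session attended, and only the time afterwards is uncovered.

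**Conclusion.** The point holds as a gap in ascertainment after the last attended session. For completers, that is about 8 of 12 calendar weeks and 2 of 18 scheduled visits from first treatment onward. For early discontinuers, it is all remaining time. The conclusion assumes that the SAP sentence is the full collection rule and that no unlisted form asks about events at weeks 8 and 12.

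The direction of error, towards undercounting late events and events linked to stopping, is a reasoned expectation. The documents give no adverse-event or dropout rate, so they cannot show how large the undercount would be, or that the safety summary would in fact mislead. This is a worthwhile and cheap improvement, not a flaw that invalidates the safety data collected during treatment.

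**What to change.** 1. Add a short open adverse-event item to the week-8 and week-12 contacts: any new or ongoing event since last contact, its date and its seriousness.
2. Use the same item at any successful contact made under the lost-to-follow-up procedure with a participant who has stopped attending.
3. Report solicited and volunteered events separately.
4. The document is dated May 2023 and is partly in the past tense, so some contacts may already have taken place. For those participants, state the window in which events were solicited.

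**Cost.** One short REDCap form. At 20 participants, the two follow-up contacts need at most 20 × 2 = 40 administrations, fewer with dropout, plus one per discontinuer reached. Each takes a few minutes, and the follow-up contacts are already planned at 45 to 60 minutes. The drawback is that some extra events will be unrelated to treatment.
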